### **5.2.7 Contraindications for Subsequent Vaccinations**

Not applicable since only one dose of vaccine will be administered in this trial.

### **5.2.8 Contraindications for Visit 2 Blood Samples**

Should a subject receive oral or injectable antibiotic therapy within 3 days prior to the second blood draw, the Investigator will postpone that blood draw until it has been 3 days (72 hours) since the subject last received oral or injectable antibiotic therapy. Postponement must still be within the timeframe for blood draw (30 to 44 days after vaccination at D0). If postponement would result in the sample collection falling outside of this timeframe, the blood sample should be collected without postponement, and it should be documented appropriately that the sample was taken less than 3 days after stopping antibiotic treatment.

### **5.2.9 Conditions for Withdrawal**

Subjects / parents / guardians will be informed that they have the right to withdraw / withdraw their child from the trial at any time.

A subject may be withdrawn from the study:

- At the discretion of the Investigator or Sponsor due to safety concerns (withdrawal) without the subject's permission
- At the request of the subject or the subject's parent / guardian (dropout)

The following will result in automatic withdrawal or exclusion of a subject from the study:

- Significant non-compliance with the protocol, based on the Investigator's judgment

The reason for a withdrawal or dropout should be clearly documented in the source documents and on the CRF.

The Investigator must determine whether voluntary withdrawal is due to safety concerns (in which case, the reason for discontinuation will be noted as "SAE" or "other AE" as appropriate) or for another reason.

Withdrawn subjects will not be replaced.

#### 5.2.10 Lost to Follow-up Procedures

In the case of subjects who fail to return for a follow-up examination, documented reasonable effort (i.e., documented telephone calls and certified mail) should be undertaken to locate or recall them, or at least to determine their health status while fully respecting their rights. These efforts should be documented in the CRF and in the source documents.

#### 5.2.11 Classification of Subjects Who Discontinue the Trial

For any subject who discontinues the trial prior to completion, the most significant reason for early termination will be checked in the CRF. Reasons are listed below from the most significant to the least significant (refer to the CRF completion guidelines for additional details and examples):

- **Serious adverse event:** To be used when a subject drops out of or is withdrawn from the study by the Investigator because of the occurrence of an SAE, as defined in [Section 9.3.2.1](#).
- **Other adverse event:** To be used when a subject drops out of or is withdrawn from the study by the Investigator because of the occurrence of an AE other than an SAE, as defined in [Section 9.3.2.1](#).
- **Non-compliance with protocol:** To be used when the Investigator withdraws a subject from the study because of failure to follow the protocol, including when it is retrospectively discovered that a subject did not fulfill the eligibility criteria. The Investigator will provide a comment as to the specific cause of non-compliance.
- **Lost to follow-up:** To be used when the Investigator withdraws a subject from the study because of failure to establish contact, as outlined in [Section 5.2.10](#). The Investigator will provide documentation that contact was attempted (i.e., return of unsigned certified letter receipt).
- **Voluntary withdrawal not due to an adverse event:** To be used when a subject drops out of the study for any reason other than those listed above.

### 5.2.12 Follow-up of Discontinuations

The site should complete all scheduled safety follow-ups and contact any subject who has prematurely terminated the trial because of an SAE, other type of AE, non-compliance with the protocol, or loss of eligibility, including definite contraindications.

For subjects where the reason for early termination was lost to follow-up or if the subject withdrew informed consent and specified that they do not want to be contacted again and it is documented in the source document, the site will not attempt to obtain further safety information.

For subjects where the reason for early termination is voluntary withdrawal, the site will attempt to contact them for the 6-month follow-up except if they specified that they do not want to be contacted again and it is documented in the source document.

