### 1.3.2 Potential Risks to Subjects

Like other vaccines, vaccination with MenACYW conjugate vaccine or Menactra® may cause injection site reactions such as pain, swelling, and erythema, or certain systemic events such as fever, headache, malaise, or myalgia.

Other common reactions after Menactra® in the studied age group include injection site induration, fatigue, arthralgia, appetite lost, and diarrhea.

There may be a rare possibility of an allergic reaction which could be severe. Prior to any vaccine injection, all known precautions should be taken to prevent hypersensitivity reactions. This includes a review of the subject's prior vaccination history with respect to possible hypersensitivity to the vaccine or similar vaccines. Epinephrine injection (1:1000) and other appropriate agents used for the control of immediate allergic reactions must be available to treat unexpected reactions (e.g., anaphylaxis).

There may be other risks for MenACYW conjugate vaccine which are not yet known.

The following additional adverse events have been very rarely reported during post-approval use of Menactra®: Guillain-Barré syndrome (GBS), transverse myelitis, acute disseminated encephalomyelitis, vasovagal syncope, facial palsy, dizziness, paraesthesia, convulsion, and hypersensitivity reactions such as anaphylactic / anaphylactoid reaction, wheezing, difficulty breathing, upper airway swelling, urticaria, erythema, pruritus, and hypotension. Because these events were reported voluntarily from a population of uncertain size, it is not possible to reliably estimate their frequency or to establish a causal relationship to Menactra® exposure.

GBS has been reported mostly in persons aged 11 to 19 years who had symptom onset within 6 weeks of administration of Menactra® (29). A retrospective cohort study carried out in the US using healthcare claims data found no evidence of increased GBS risk following Menactra® vaccination. The study was able to exclude all but relatively small incremental risks (30).

A review by the Institute of Medicine (IOM) found inadequate evidence to accept or reject a causal relationship between tetanus toxoid-containing vaccines and GBS (31). The IOM found evidence for a causal relation between tetanus toxoid-containing vaccines and brachial neuritis (32). Arthus reactions are rarely reported after vaccination and can occur after tetanus toxoid-containing vaccines (33).

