## 5 Investigational Plan

### 5.1 Description of the Overall Trial Design and Plan

#### 5.1.1 Trial Design

This is a Phase III, modified double-blind, randomized, parallel-group, active-controlled, multi-center study to evaluate immune lot consistency of MenACYW conjugate vaccine, evaluate the immune non-inferiority versus Menactra®, and describe the safety and additional immunogenicity of these study vaccines in adolescents and adults aged 10 to 55 years in the United States.

Healthy, meningococcal-vaccine naïve adolescents and adults will be randomized in a 3:3:3:2 ratio to the following groups:

- Group 1: MenACYW conjugate vaccine (Lot 1)
  - Group 1a: 400 subjects 10 to 17 years of age
  - Group 1b: 500 subjects 18 to 55 years of age
- Group 2: MenACYW conjugate vaccine (Lot 2)
  - Group 2a: 400 subjects 10 to 17 years of age
  - Group 2b: 500 subjects 18 to 55 years of age
- Group 3: MenACYW conjugate vaccine (Lot 3)
  - Group 3a: 400 subjects 10 to 17 years of age
  - Group 3b: 500 subjects 18 to 55 years of age
- Group 4: Menactra®
  - Group 4a: 300 subjects 10 to 17 years of age
  - Group 4b: 300 subjects 18 to 55 years of age

All subjects will provide blood samples for immunogenicity assessment at baseline (pre-vaccination) and at 30 to 44 days post-vaccination.

Solicited AE information will be collected for 7 days after vaccination, unsolicited AE information will be collected from Visit 1 (Day [D] 0) to Visit 2 (D30 [+14 days]), and SAE information will be collected from D0 through D180 (+14 days) after vaccination.

Medically-attended adverse events (MAAEs) will be collected throughout the study from Visit 1 to Visit 2 (as part of the collection of unsolicited AE information) and from Visit 2 through D180 (+14 days) (as MAAEs).

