- 14) Remind the subject or the subject's parent / guardian to notify the site in case of an SAE.
- 15) Complete the relevant CRF pages for this visit.

Telephone Call 1 (8 to 10 days after Visit 1)

**Note:** If Day 08 falls on a weekend or a holiday, the telephone call may be made on the following business day. If the subject or the subject's parent / guardian is not available, the study staff should document the attempts to make contact.

- 1) Record relevant information concerning the subject's health status on the telephone contact form. If an SAE occurred, follow the instructions in [Section 10](#) for reporting it.
- 2) Remind the subject or the subject's parent / guardian to do the following:
  - Complete the D0 to D07 pages of the diary card
  - Complete the remaining pages of the diary card and bring them to Visit 2
  - Notify the site in case of an SAE

Visit 2 (30 days [+14 days] after Visit 1): Collection of Safety Information and Blood Sample

- 1) Review the pages of the diary card with the subject or the subject's parent / guardian, including any AEs, medications, or therapy that occurred since vaccination. The subject or subject's parent / guardian must return the diary card.
- 2) Review the temporary contraindications for blood sampling (see [Section 5.2.8](#)).
- 3) Obtain the blood sample (see [Section 7](#) for detailed instructions regarding the handling of blood samples).
- 4) Give the subject or the subject's parent / guardian an MA.
- 5) Complete the termination record of the CRF.
- 6) If the subject or the subject's parent / guardian does not return for Visit 2, and the diary card is not received at the site, site personnel will contact the subject or the subject's parent / guardian by telephone. During the telephone call, the subject or the subject's parent / guardian will be reminded to return the diary card to the study site. Telephone calls will be documented on the Telephone / Interview Record. If the study personnel are unable to contact the subject or the subject's parent / guardian with 3 attempts, the study personnel will follow instructions given in [Section 5.2.10](#).

Safety Follow-up Telephone Call 2 (180 days [+14 days] after Visit 1): Collection of SAEs and MAAEs

Review the MA and ask the subject or the subject’s parent / guardian if the subject has experienced any SAE in the time since the vaccination that has not been reported to the study personnel and / or any MAAE.

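### Section 5.2.12 ends all safety contact for subjects coded lost to follow-up, although they never refused it, while voluntary withdrawals who have not refused are still called at 6 months

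*Protocol*

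**What the plan says.** Protocol Section 5.2.12 sorts discontinued subjects into three classes.

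- **Terminated for an SAE, another AE, non-compliance or loss of eligibility:** the site completes every scheduled safety follow-up.
- **Voluntary withdrawal:** in this class, "the site will attempt to contact them for the 6-month follow-up except if they specified that they do not want to be contacted again", with the refusal documented.
- **Lost to follow-up, or consent withdrawn with a documented wish not to be contacted:** "the site will not attempt to obtain further safety information". The sentence opens "For subjects where the reason for early termination was lost to follow-up or if the subject withdrew informed consent". The refusal condition follows the consent-withdrawal limb and is not attached to the lost-to-follow-up limb.

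The route to that code runs through three other sections. In Section 5.1.4 (Visit 2), if the subject does not return and the diary card is not received, the site telephones. If staff "are unable to contact the subject" or the parent or guardian in 3 attempts, they go to Section 5.2.10, which asks for documented calls and certified mail to find the subject or at least learn their health status. Section 5.2.11 then codes failure to establish contact as lost to follow-up.

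Elsewhere the plan describes full follow-up with no such exception. Section 5.1.1 says "SAE information will be collected from D0 through D180 (+14 days) after vaccination" and carries MAAE collection to the same point. Section 5.1.3 has staff telephone at 6 months. The Synopsis gives that call to subjects in all groups. SAP Table 5.2 lists SAEs and MAAEs up to the 6-month follow-up for all subjects in Groups 1 to 4.

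**The concern.** Two kinds of subject receive no further call: those who asked for that, and those who could not be found at one point in the trial. The documents give no reason for treating them alike. The effect is that someone who chose to leave is called at 6 months, and someone who never refused is not. Failure to reach a subject after a missed Visit 2 does not show that the subject is still unreachable at Day 180.

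What is at stake is the completeness of the 6-month safety description. The Safety Analysis Set (Protocol 12.2.2, SAP 5.2.2) requires one dose and any safety data, with no minimum follow-up. Missing safety data are not replaced (Protocol 12.3.1, SAP 5.3.1). The SAP defines no separate denominator of subjects who completed the 6-month contact. A subject last contacted at Call 1 can therefore enter the SAE and MAAE percentages as having had no event. Illness can itself cause a missed visit, so the loss need not be random.

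**Working it through.** **1. Which subjects the rule reaches.** Four conditions must hold together: Visit 2 missed, diary card not received, telephone attempts failed, and the Section 5.2.10 search failed. The subject is then coded lost to follow-up. The refusal condition cannot sensibly be read back onto this class, because a subject who cannot be reached has had no occasion to refuse.

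**2. What collection remains.** Scheduled contacts after Visit 1 are Call 1 (Day 8 to 10), Visit 2 (Day 30 to 44) and Call 2 (Day 180 to 194). With Visit 2 missed and Call 2 barred, Call 1 is the last scheduled contact that could have taken place. The memory aid is handed out only at Visit 2. Before Visit 2, MAAEs are recorded on the diary card, which here was not returned, and Call 1 is directed at unreported SAEs. MAAE capture may therefore be poorer than SAE capture.

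**3. Days without active collection.**

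- Last contact Day 10, end Day 180: 180 − 10 = 170; 170/180 = 94%.
- Last contact Day 8, end Day 180: 180 − 8 = 172; 172/180 = 96%.
- End Day 194: 194 − 10 = 184 (95%) and 194 − 8 = 186 (96%).

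**4. The plan's own dropout figure.** The Synopsis allows 10%: 900 × 0.90 = 810 evaluable per lot and 600 × 0.90 = 540 for Menactra. Both match. The total is 3 × 900 + 600 = 3300, and 10% of that is 330 subjects (270 MenACYW, 60 Menactra). This is an allowance for evaluable subjects in the immunogenicity sample size. It is not a lost-to-follow-up rate, and the documents give no such rate.

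**5. Range for the size.** Assume that 2%, 5% or 10% of subjects are affected, equally across arms, each with last contact at Day 10. The share of planned follow-up days without active collection is (subjects × 170)/(3300 × 180). For MenACYW, the one-sided 95% upper bound on an event rate with zero events is 1 − 0.05^(1/n), where n counts only the subjects followed.

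| Assumed share | Subjects | Share of follow-up days | MenACYW n | Zero-event bound |
|---|---|---|---|---|
| 0% | 0 | 0% | 2700 | 0.111% |
| 2% | 66 | 1.9% | 2646 | 0.113% |
| 5% | 165 | 4.7% | 2565 | 0.117% |
| 10% | 330 | 9.4% | 2430 | 0.123% |

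At the upper limit the bound rises by 0.123 − 0.111 = 0.012 percentage points. This measures lost precision only. It does not measure bias if events are more common among the subjects lost, and the documents give nothing from which to estimate that.

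**The case against.** **It is an exception, not a contradiction.** Section 5.1.1 and the Synopsis set a general schedule, and Section 5.2.12 is the specific rule for people who have left. This stands. A reader might infer that the protocol contradicts itself, but the exclusion of subjects who refuse contact departs from the same schedule and nobody would call that an error. What remains is that the lost-to-follow-up exception has no stated reason and is not mentioned where full follow-up is described.

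**Data after Day 10 may still arrive.** This also stands. Missing Visit 2 does not by itself trigger the rule. A returned diary card, or a subject reached during the search, supplies later data. Subjects are told to report SAEs at any time, and the rule stops outbound attempts, not receipt of reports. No deadline is set for the code, so a site may search for some time before using it. The gap is in active collection, and 170 days is its upper end.

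**Informative loss is partly handled.** If the site learns that a subject left because of an SAE, Section 5.2.11 ranks that reason above lost to follow-up, and Section 5.2.12 then requires full follow-up. For adolescents a parent or guardian is a second contact. The concern survives only where nobody is reached.

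**The 6-week text invites over-reading.** Section 1.3.2 mentions Guillain-Barré cases "who had symptom onset within 6 weeks of administration of Menactra". One might infer that most of a planned surveillance window goes uncovered. The text is background on reports after the licensed comparator and sets no such window for this trial.

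**Safety is descriptive and the bound barely moves.** True, and it limits the weight of the point. Keeping partly followed subjects in the denominator also comes from the Safety Analysis Set definition, not from Section 5.2.12.

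**Conclusion.** The point holds as an unjustified asymmetry in safety follow-up that is worth correcting. For a subject who meets all the conditions for the code, up to about 170 of 180 days can pass without active SAE or MAAE collection, while that subject remains in the 6-month denominators.

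The number of such subjects is unknown. Treating all 330 subjects in the 10% allowance as lost to follow-up is an upper limit, not an expectation, and even then the MenACYW zero-event bound rises only from 0.111% to 0.123%. That comparison assumes equal loss across arms, no information from the lost subjects, and that the extra call would recover all of them, which it would not. The case therefore rests on unequal treatment of subjects who never refused contact and on possible informative loss, not on lost precision. The primary immunogenicity conclusions are not affected.

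The documents do not support the stronger inference that every subject who misses Visit 2 has no safety data after Day 10.

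**What to change.** In Protocol Section 5.2.12, limit the instruction to make no further safety contact to subjects who asked not to be contacted, with that request documented. For subjects coded lost to follow-up who did not refuse, require the Day 180 (+14) Call 2 attempt for SAEs and MAAEs, as already required for voluntary withdrawals. Reconcile the section with Sections 5.1.1 and 5.1.3, so that any exception to 6-month collection that remains is stated there too.

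The cost is a short protocol amendment and one round of telephone attempts per affected subject, using a procedure that already exists. Some calls will fail, because these subjects have already proved hard to reach. The change does not alter the Safety Analysis Set definition; it reduces the number of subjects in it for whom no 6-month contact was tried.

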### 5.2.13 Follow-up and Reporting of Pregnancies

Pregnancy is an exclusion criterion for enrollment in this study, but a subject could potentially become pregnant during her participation. In case of pregnancy and if at least one dose of the study vaccine(s) has been administered, the subject will not be discontinued from the trial and will be followed for safety assessment (and may be followed for immunogenicity assessment, if applicable). However, no additional vaccination will be administered.

All pregnancy cases should be reported if they occurred during the study, and during the 6-month follow-up period or if the start date of the pregnancy cannot be determined. To report the pregnancy case, the Investigator must fill out a Pregnancy Reporting Form in the electronic data capture (EDC) system and send it to the Sponsor within 1 month of identifying a pregnancy case.

Study staff must then maintain contact with the subject to obtain information about the outcome—i.e., details about the delivery and the newborn, or about pregnancy termination—and must update the electronic Pregnancy Reporting Form. This information should be provided to the Sponsor within 1 month of delivery.

Pregnancy itself is not considered an AE, but any complications during pregnancy are to be considered as AEs, and in some cases could be considered SAEs. Spontaneous abortions, fetal death, stillbirth, and congenital anomalies reported in the baby are always considered as SAEs, and the information should be provided to the Global Pharmacovigilance (GPV) Department regardless of when the SAE occurs (e.g., even after the end of the trial).

## 5.3 Safety Emergency Call

If, as per the Investigator's judgment, a subject experiences a medical emergency, the Investigator may contact the Sponsor's RMO for advice on trial related medical question or problem. If the RMO is not available, then the Investigator may contact the Call Center - available 24 hours a day, 7 days a week - that will forward all safety emergency calls to the appropriate primary or back-up Sanofi Pasteur contact, as needed. The toll-free contact information for the Call Center is provided in the Operating Guidelines.

This process does not replace the need to report an SAE. The investigator is still required to follow the protocol defined process for reporting SAEs to GPV (please refer to [Section 10](#)).

In case of emergency code-breaking, the Investigator is required to follow the code-breaking procedures described in [Section 6.4](#).

## 5.4 Modification of the Trial and Protocol

Any amendments to this trial plan and protocol must be discussed with and approved by the Sponsor. If agreement is reached concerning the need for an amendment, it will be produced in writing by the Sponsor, and the amended version of the protocol will replace the earlier version. All substantial amendments (e.g., that affect the conduct of the trial or the safety of subjects) require IEC / IRB approval, and must also be forwarded to regulatory authorities.

An administrative amendment to a protocol is one that modifies some administrative or logistical aspect of the trial but does not affect its design or objectives or have an impact on the subjects' safety. Administrative changes do not require IEC / IRB approval; however, the IEC / IRB must be notified whenever one is made.

The Investigator is responsible for ensuring that changes to an approved trial, during the period for which IEC / IRB approval has already been given, are not initiated without IEC / IRB review and approval, except to eliminate apparent immediate hazards to subjects.

